4.4 Acceptance Criteria

Since this protocol applies to a retrieval analysis and not to testing there are no acceptance criteria. Only the current condition of the received retrievals, including the identification of structural failures, will be documented.

5 REPORTING

A Zimmer Research Report (ZRR) will be created to document the retrieval analysis of every received case.

A copy of the ZRR(s) will be sent to the Zimmer Spine Clinical Affairs Section 522 Clinical Study Manager for analysis and inclusion in the Dynesys Section 522 Post-Market Surveillance Study final report documenting device failure, patient demographics, and clinical circumstance. Any trends or correlations between device failure, patient demographics, and clinical circumstances will be documented in the Section 522 final study report.

A summary report of the received cases will be written after 12, 24, and 36 months. This report should summarize all the findings and results from the retrieval analysis, including identification of structural failures. The report should also include a section to propose modification of the test

protocol for the retrieval analysis if necessary. This may include additional test(s), to omit existing tests, or to perform tests only after a certain time *in-vivo*.

7 APPENDICES

8 REVISION HISTORY

In Revision 1 of this protocol the following changes were made:

- On the cover page a signatory for Regulatory Affairs had to be updated.
- On the cover page a signatory for Research had to be updated.
- On page 2 under chapter 3 Handling of Retrievals section Revision surgery it was added that patient consent is only necessary for patients outside the US.
- On page 3 under chapter 3 Handling of Retrievals section Note it was added that patient consent is only necessary for patients outside the US.
- On page 9 under chapter 6 References in reference [1] the version of the ISO was updated and in reference [8] the word spinal was deleted.

IMAGING PROTOCOL:
Post Market Surveillance for the Dynesys® Spinal System, Assessing Safety and Fusion.

CMU2010-10S
September 20, 2010

Sponsor:
Zimmer Spine, Inc.
[name]
[name]

I. STUDY PURPOSE

To assess the safety profile and fusion rates following posterior lateral fusion with the *Dynesys*® Spinal System as an adjunct to fusion compared to literature control.

II. RADIOGRAPHIC IMAGING

Subjects will undergo standard evaluations at specified pre- and post-operative time points. The radiographic imaging schedule is presented in Table 1 below. Plain film imaging will include Neutral Lateral, Neutral AP and Flexion-Extension.

Table 1: Radiograph Schematics

	Pre-Op	Surgery	6M	12M	24M	Annual
	-4 weeks		±4 weeks	±8 weeks	±8 weeks	±8 weeks
Radiographs (AP, NL, Flexion, Extension)	X		X	X	X	X
Radiographic Assessment	X		X	X	X	X

A. Quality Assurance

Unless limited by subject or equipment constraints, plain radiographs will be obtained with the subject in a standing position. The subject will be instructed to move in the directed position to the maximum extent possible. The radiology technician and study coordinator will ensure that the views exhibit minimal out-of-plane effects, that all relevant levels are visible and that the films are properly labeled.

The films will be used to evaluate device condition and to detect the presence of device-related complications including retrolisthesis, spondylolisthesis, instability, degeneration, radiolocency, bridging bone and fusion status. The radiographs will also be used to quantify certain radiographic parameters including translations, angular range of motion and bridging bone.

Quantitative and qualitative radiographic assessments will be collected pre-operatively and at the follow-up intervals through 24 months and annually thereafter until the last patient has completed follow-up.

III. DATA COLLECTION & TRANSMITTAL

The investigational sites will produce the films identified in Table 1 and will send via Fed Ex to Zimmer Spine, Clinical Affairs, [name] within 15 days of evaluation, as stated in the protocol.

A. Image Collection

Sites will label each film and film jacket and/or CD and disc envelope with the patient ID, visit ID (PreOp, 6M, 12M, 24M, annual), the visit date and the views (AP, NL, Flexion, Extension). The label should be attached to the film in such a way that it does not obscure the anatomy. If possible, the film label should be placed over the patient identifiers to mask this information. It may be necessary to redact the patient identifiers by other means if the film label fails to achieve this purpose. Additionally, be sure to identify the patient's right and left side. This is mandatory on AP

views.

Images for specific subject visits should be stored on a single film or CD. If possible, a single CD should contain only the images obtained during a single visit. It is recommended that images be stored in DICOM format.

B. Shipment

All digital images and plain films shipped to Zimmer Spine must be accompanied with a memo stating the inventory of all images contained in the shipment. Images will not be returned to the site, therefore ensure all copies are made prior to shipment.

C. Data Management

Upon receipt, Zimmer Spine Data Management will verify the content and labeling of the films, verify the visit dates to ensure that all films are dated chronologically by designation, verify the visit views to ensure that all views are correctly labeled and that there are no missing films, verify film receipt logs to ensure that each set of films is stored and accounted.

Access to films and associated study data will be restricted to authorized personnel only.

Data Management will send an inventory report, case report forms and radiographs to independent reviewers every six months for review.

IV. REVIEWERS

The first assessment will be completed at the site by a radiologist. The second assessment of radiographic bridging and device condition will be performed by independent radiographic reviewers. The independent reviewers shall be a board-certified, fellowship-trained and practicing radiology with no financial interest in Zimmer Spine.

The reviewers shall be fully trained on the schedule of radiographic assessments and the classification system for performing each assessment. The reviewers shall be trained on the radiographic features of the treatment, its design, the clinical indications for its use and the relevant inclusion/exclusion criteria. The independent reviewers will not have access to clinical outcomes data when conducting the assessments.

All independent reviewers' determinations regarding the bone bridging, fusion status and additional observations are final and supersede preliminary judgments made by each site investigator.

[figure not shown]
V. DIAGRAM AND DESCRIPTION OF MEASUREMENTS

The following descriptions summarize how the measurements will be performed. Data will be collected on paper case report forms provided to the reviewers.

A. Disc Angle

Disc Angle is the angle formed between the endplates of adjacent vertebrae as shown in Figure 1. Disc Angle will be measured on neutral lateral radiographs to assess local segmental lordosis. Disc Angle will also be measured on flexion and extension radiographs to assess angular range of motion. Disc Angle will be reported in units of degrees.

[figure not shown]
Figure 1: Disc Angle Diagram

B. Angular Motion

Angular range of motion will be calculated from lateral flexion-extension radiographs in accordance with Figure 2. As described above, Disc Angle is the angle between the endplates of adjacent vertebrae. The *change* in Disc Angle from flexion to extension determines the angular range of motion. Angular Motion will be reported in units of degrees.

[figure not shown]
Figure 2: Angular Motion Diagram

C. Translational Motion

Translational motion will be calculated from flexion-extension radiographs in accordance with Figure 3. Translational motion is defined as displacement of the posterior-inferior corner of the superior vertebra in a direction defined parallel to the superior endplate of the inferior vertebra. Translational Motion will be reported in units of millimeters.

Figure 3: Translational Motion Diagram

D. Bridging Bone

Bony Bridging will be graded as "Absent, Present or Unclear" in accordance with the definitions provided below. Bridging will be defined as a continuous connection of mineralized tissue from the superior to the inferior vertebral body.

Absent: Absence of continuous bridging bone from endplate to endplate

Present: Presence of continuous bridging bone from endplate to endplate

Unclear: No determination or absence or presence of continuous bone bridging can be made based on the provided radiographs

There is no scientific consensus concerning the minimum threshold of bridging required to classify a level as solidly bridged. Therefore, discretion will be left to the radiologist to determine whether sufficient bridging exists to render an affirmative assessment.

E. Fusion Status

Fusion Status will be graded as 'Fused or Not Fused'. Fusion Status will be derived from a logical analysis of the following factors: bony bridging, angular motion and translational motion.

Not Fused: No evidence of bridging bone between the involved vertebral endplates and $\geq 5^\circ$ total angular motion and ≥ 3 mm translational motion

Fused: Evidence of bridging bone between the involved vertebral endplates and $<5^\circ$ total angular motion and <3 mm translational motion

Fusion Status will be reported for each treated level.

F. Other Radiographic Observations

Additional incidental observations or noteworthy findings will be documented at the radiologist's discretion and may include observations of screw/device loosening, lucency, malplacement or broken. Additional observations of spondylolysis, retrolistesis, degeneration, fracture and arthrodesis will be identified. Clarifying remarks regarding the assessments will also be provided, including the location/type of failure/condition.

Dynesys® Spinal System and the Zimmer® DTO™ Implant Instructions for Use

Important information for the operating surgeon

Zimmer GmbH
P.O. Box
[name]
[contact]
[contact]
www.zimmer.com

Manufacturer:
Zimmer GmbH
[name]
[name]

Distributed in the USA by:
Zimmer Spine, Inc.
[name]
[name]
[contact]
[contact]
[contact]

Art. No. D011 500 217 - e - Ed. 10/09

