When the *Dynesys Spinal System* and the *OPTIMA ZS Spinal System* are used on contiguous levels, they must be used with the *Zimmer DTO Implant*, rod-cord combination implant, and the *U & I Corporation OPTIMA ZS Transition Screw*. The indications for use for each level is as specified for each system.

Dynesys is comprised of a variety of pedicle screw sizes, tensioning cords and longitudinal spacers that are uniquely fitted for each individual case.

III. SUBJECT SELECTION

Patients participating in this study will be recruited from each investigator's standard patient population. All patients who meet the inclusion/exclusion criteria will be consecutively enrolled.

A. Inclusion Criteria

Patients must meet all of the following criteria to be enrolled into the study:

1. Patients must be skeletally mature between the ages of 20-80
2. Candidate for a posterior lateral fusion between T1-S1 with autograft
3. Degenerative spondylolisthesis with evidence of neurologic impairment, or failed previous fusion (pseudarthrosis)
4. Symptoms of leg and/or back pain
5. Non-responsive to conservative/non-surgical treatment for at least three (3) months
6. Must be willing and able to comply with study requirements; including complete necessary study paperwork and return for required follow-up visits.

B. Exclusion Criteria

Patients who meet any of the following criteria should not be enrolled into the study:

1. Active systemic or local infection
2. Obesity
3. Use of interbody device
4. Pregnancy
5. Mental illness
6. Incarceration
7. Alcohol or drug abuse
8. Severe osteoporosis or osteopenia
9. Use in the cervical spine
10. Sensitivities/allergy to metals, polymers, polyethylene, polycarbonate urethane and polyethylene terephthalate
11. Soft tissue deficit not allowing sound closure
12. Any medical or physical condition that would preclude the potential benefit of spinal implant surgery
13. Congenital abnormalities, tumors or other conditions that would prevent secure component fixation that has the potential to decrease the useful life of the device
14. Active malignancy or other significant medical comorbidities
15. Any medical or mental condition which would put the patient at high risk due to the severity of surgery
16. Inadequate pedicles of the thoracic, lumbar and sacral vertebrae
17. Patient unwilling or unable to follow postoperative instructions

IV. STUDY PROCEDURES AND DATA COLLECTION

Table 1: Study Schematics

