- *Operative/Discharge Evaluation*: dates of admission, surgery and discharge, operative level, estimated blood loss, duration of surgery, discharge medications, device implant specifics, reason for device choice, autograft harvest and placement and neurological assessment
- *Adverse Event (as needed)*: record events, device relationship, date of complication, severity, outcome and treatment details
- *Protocol Deviation (as needed)*: deviation and reason
- *Patient Discontinuation (as needed)*: reason for discontinuation and date

C. Post-Operative – 6 month (+/- 4 weeks)

The following procedures and assessments will be performed following surgery.

- *Patient Assessment*: pain level and satisfaction
- *Oswestry Disability Index (ODI)*: functional assessment
- *Clinician Evaluation*: neurological assessment (sensory and motor testing, reflex testing and straight leg raising), medication usage, employment status, tobacco use and surgical results
- *Radiographs*: A/P, N/L, flexion, extension
- *Radiographic Assessment*: overall and unilateral fusion success (translation motion <3mm, angulation motion <5° and bridging bone) will be assessed by site radiologist and an independent reviewer
- *Adverse Event (as needed)*: record events, device relationship, date of complication, severity, outcome and treatment details

- *Protocol Deviation* (as needed): deviation and reason
- *Patient Discontinuation* (as needed): reason for discontinuation and date

D. Post-Operative – 12, 24 month (+/- 8 weeks)

The following procedures and assessments will be performed following surgery.

- *Patient Assessment*: pain level and satisfaction
- *Oswestry Disability Index (ODI)*: functional assessment
- *Clinician Evaluation*: neurological assessment (sensory and motor testing, reflex testing and straight leg raising), medication usage, employment status, tobacco use and surgical results
- *Radiographs*: A/P, N/L, flexion, extension
- *Radiographic Assessment*: overall and unilateral fusion success (translation motion <3mm, angulation motion <5° and bridging bone) will be assessed by site radiologist and an independent reviewer
- *Adverse Event (as needed)*: record events, device relationship, date of complication, severity, outcome and treatment details
- *Protocol Deviation* (as needed): deviation and reason
- *Patient Discontinuation* (as needed): reason for discontinuation and date

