Decorticate the posterior elements as necessary. Place bone graft to achieve the desired fusion.

[figure not shown]

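### Appendix B defines bridging bone in terms that describe interbody fusion, in a trial of posterolateral fusion, so the primary endpoint may be misgraded or read inconsistently

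*Combined protocol and SAP*

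**What the plan says.** Section V.B makes fusion status at Month 24 the primary endpoint. Success needs bridging bone, angulation under 5° and translation under 3 mm at the treated levels. It does not say where the bone must lie.

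Appendix B supplies the operational definition. V.D opens with "Bridging will be defined as a continuous connection of mineralized tissue from the superior to the inferior vertebral body", and the grade Present means "Presence of continuous bridging bone from endplate to endplate". In V.E both grades turn on "evidence of bridging bone between the involved vertebral endplates": Fused requires it together with motion below both limits, and Not Fused requires its absence together with motion at or above both limits.

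On the amount of bone, V.D says that "discretion will be left to the radiologist to determine whether sufficient bridging exists to render an affirmative assessment". On authority, Appendix B IV says that the independent reviewers' "determinations regarding the bone bridging, fusion status and additional observations are final and supersede preliminary judgments" made at the site.

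On the operation, Section III.A enrols candidates for posterior lateral fusion with autograft, and III.B item 3 excludes "Use of interbody device". The Dynesys LIS technique ends with "Decorticate the posterior elements as necessary. Place bone graft to achieve the desired fusion", and the DTO technique has the same step. Sections IV.C to IV.E ask for "overall and unilateral fusion success" at each postoperative visit.

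**The concern.** Appendix B uses the endplate as a landmark of the disc space: V.A forms the Disc Angle from the endplates of neighbouring vertebrae. Bone running from body to body and endplate to endplate is therefore, on its natural reading, interbody bone. The enrolled operation is a posterolateral fusion, and a unilateral result fits a left or right posterolateral mass much better than bone between endplates.

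Bridging is a required component of the primary endpoint, and Appendix B is the text to which the final readers work. A reader who applies it literally may withhold credit from a solid posterolateral mass. A reader who applies surgical common sense may give credit. The measured rate would then depend on the reader as well as the device, and it feeds a non-inferiority test with a 10-point margin. Repairing the Fused / Not Fused logic alone would leave the location unresolved.

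**Working it through.** **The texts side by side**

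| Source | What it implies about the site of bone |
|---|---|
| Appendix B V.D and V.E | Between vertebral bodies, endplate to endplate |
| Section V.B | No location given |
| Sections III.A and III.B | Posterior lateral fusion with autograft; no interbody device |
| LIS and DTO techniques | Posterior elements decorticated, then graft placed; no disc-space grafting step |
| Sections IV.C to IV.E | Fusion assessed overall and unilaterally |

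No legible part of the documents defines bridging at a posterolateral site.

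**The plan's own figure.** Section V.G gives a literature rate of 80.6%, a difference of 10%, alpha 0.05, power 80% and n = 134, or 168 with 20% attrition. A one-sample test of 0.806 against 0.706 at two-sided 0.05 reproduces it:

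n = [1.960·√(0.806×0.194) + 0.842·√(0.706×0.294)]² / 0.10² = 134.2; then 134/0.80 = 167.5, rounded up to 168.

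The bridging definition does not enter, so correcting it leaves the sample size unchanged.

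**If misgraded patients count as failures.** Assume true fusion of 80.6%, n = 134, and a share m of truly fused patients not credited. The documents do not give m. The expected observed rate is 0.806 × (1 − m): 76.6% at m = 5% and 72.5% at m = 10%.

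The rule is that the lower 95% limit of the difference exceeds −10%. Using a Wald limit and exact binomial probabilities:

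- Benchmark fixed: p̂ − 0.806 − 1.96·√(p̂(1−p̂)/134) > −0.10. With 104 fused the limit is −10.05% and fails; with 105 it is −9.2% and passes.
- Benchmark SE of 2.6% (Section V.B) included: add 0.026² under the root. With 106 fused the limit is −10.06% and fails; with 107 it is −9.2% and passes.

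| Assumed m | Observed rate | Chance of success, benchmark fixed | Chance of success, SE included |
|---|---|---|---|
| 0 | 80.6% | 78% | 64% |
| 5% | 76.6% | 36% | 22% |
| 10% | 72.5% | 8% | 3% |

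A normal approximation gives 83%, 37% and 7% with the benchmark fixed, and 64%, 26% and 6% with the SE included. Above m = 1 − 0.706/0.806 = 12.4%, the expected observed rate lies below 70.6% even though true fusion equals the benchmark.

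**If they are treated as undetermined.** A level graded Absent with little motion is neither Fused nor Not Fused under V.E. Section V.B drops patients whose Month 24 status is missing and who were not fused earlier. If only misgraded fused patients are dropped, the rate is 0.806(1 − m) / [0.806(1 − m) + 0.194]:

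- m = 5%: 0.7657/0.9597 = 79.8%
- m = 10%: 0.7254/0.9194 = 78.9%

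Truly unfused levels held stiff by the implant would fall into the same gap. If a share u of unfused patients is also dropped, 0.194 becomes 0.194(1 − u), and the rate exceeds 80.6% whenever u > m. The sensitivity analysis in V.B would count all the dropped patients as not fused.

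**The case against.** The case for leniency has several parts.

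- **Graft site.** The exclusion names an interbody device, not disc-space graft. The technique manuals decorticate the posterior elements but do not say where the graft goes. The Operative/Discharge form offers discectomy/nucleotomy and records where autograft was harvested, but has no legible item for where it was placed, although Section IV.B lists placement. A reader might infer that the endpoint looks for bone where none is grafted. That is a reasonable inference, but the documents do not state it.
- **Reader behaviour.** The endplate phrase could be taken as the cranio-caudal span to be bridged. Appendix B IV has readers trained on the classification and on the radiographic features of the treatment, and III.A makes side marking mandatory on AP views. It is therefore too strong to say that every literal reader would grade a solid posterolateral mass as Absent. This softens the concern but does not remove it, because the discretion granted covers sufficiency and not site.
- **Reader form.** The radiographic assessment form is not in the supplied text. It may already grade left and right, so a missing side-specific grade cannot be shown.
- **Benchmark.** One might infer that 80.6% is a posterolateral rate and that the comparison must fail. Section V.G calls it a lumbar fusion rate, and nothing says how the source studies defined fusion. Comparability cannot be shown either way.
- **Section V.B.** It gives no location and is not itself wrong. The conflict sits in Appendix B.

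All of these limits stand. None supplies a posterolateral definition of bridging.

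**Conclusion.** The concern holds as a wording conflict in Appendix B that reaches the primary endpoint. V.D and V.E describe interbody bridging, the trial performs posterolateral fusion, and the final readers are given no discretion over location. A solid posterolateral mass may go uncredited, and readers may differ.

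The size rests on assumptions: the misgraded share is not in the documents, and the fall from 78% to 36% (or from 64% to 22% with the benchmark SE) at 5% misgraded requires that those patients count as failures. It is tempting to infer a fixed bias against the device. The documents do not support that, since the same levels can be dropped as undetermined, with a smaller fall or even a rise in the rate. An endpoint whose error could run either way, depending on reader and on handling, is still a weak basis for a non-inferiority claim. Because the repair is cheap and the component is required for success, it should be made before any film is read.

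**What to change.** In Appendix B V.D and V.E, replace the body-to-body sentence and both endplate phrases with continuous bridging bone across the posterolateral graft between the adjacent treated vertebrae. Grade it by level and by side, so that overall and unilateral status can be derived, and state which film view is read for bridging. Have Section V.B refer to that definition. Check that the radiographic reader form matches, and train readers on the revised text before the first reads. State how the literature studies defined fusion where this is known, so that the comparison with 80.6% can be judged.

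The cost is wording and reader training, with a form edit only if the form does not match. There are no added films or readers, and the sample size stays at 134 (168 enrolled).

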To assure that baseline characteristics of the history control data are similar to those found in the experimental data, the demographic characteristics from the study data will be reviewed to confirm that the characteristics of age, gender, smoking status, and preoperative diagnosis in the test data are similar to the data that existed for the historical control data. The rate of males and rate of smokers will be checked against the 95% confidence interval found in the point estimate table. The distribution of preoperative diagnoses will be tested for no difference between the historical control and the test group. The average age will be checked to assure that it is in the range from 41 to 75. If any differences are noted, patients with extreme data will be removed until the rates and means of the test population do reside within the bounds determined by the meta-analysis. If needed, more patients will be enrolled in the test group to assure that the sample size is sufficient for inferential testing.

B. Primary Analysis: Fusion Status

Fusion success will be defined as evidence of bridging bone and angulation of <5° and translation of <3mm at treated levels at 24 months. Radiographic assessment will determine for each patient a fusion status, either fused or not fused. The primary endpoint is fusion status at Month 24. Efficacy will be confirmed by the achievement of fusion in the experimental group when compared to the rate established in a literature control. Normand (1999) provided the direction for the meta-analysis¹. The details of that analysis included creating population mean and variance estimates using a weight of the inverse of the variance. (See pp. 335-336 for complete description of the algorithm) A point estimate of 80.6% with a standard error of 2.6% was established. The 95% confidence interval for this point estimate is (75.0%, 86.3%).

If Month 24 fusion status cannot be determined, but fusion was determined to have occurred earlier, the Month 24 status will be considered fused. Otherwise, subjects without earlier fusion who are missing Month 24 values will be excluded from primary analysis.

For the purpose of a sensitivity analyses, all subjects excluded as described above for a missing Month 24 fusion status will be defined as not fused.

C. Primary Analysis: Safety Endpoints and Evaluation

Subjects will be clinically evaluated for adverse experiences and functional outcomes over the course of 24 months.

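### The imaging protocol's rule for a failed fusion requires all three criteria to fail together, so six of eight finding patterns have no status and the primary endpoint definition is contradicted

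*Combined protocol and SAP*

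**What the plan says.** Appendix B, V.E, sets the grading of each treated level: "Fusion Status will be graded as 'Fused or Not Fused". The grade is not a free judgement: "Fusion Status will be derived from a logical analysis of the following factors: bony bridging, angular motion and translational motion". The fused grade needs bridging bone, angular motion below 5° and translation below 3 mm, all together. The not-fused grade reads "No evidence of bridging bone between the involved vertebral endplates and" and continues with angular motion of at least 5° and translation of at least 3 mm, also all together.

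Appendix B, V.D, adds a third bridging grade, Unclear: "No determination or absence or presence of continuous bone bridging can be made based on the provided radiographs". V.E does not say which status an Unclear level receives.

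Section V.B defines the primary endpoint: "Fusion success will be defined as evidence of bridging bone and angulation of <5° and translation of <3mm at treated levels at 24 months". It treats the outcome as binary: "Radiographic assessment will determine for each patient a fusion status, either fused or not fused". The visit descriptions in Section IV (C to E) use the same three criteria: "overall and unilateral fusion success (translation motion <3mm, angulation motion <5° and bridging bone").

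For an unresolved Month 24 result, V.B states: "If Month 24 fusion status cannot be determined, but fusion was determined to have occurred earlier, the Month 24 status will be considered fused". Patients with no earlier fusion and a missing Month 24 value leave the primary analysis. One sensitivity analysis scores those excluded patients as not fused. Appendix B, IV, makes the independent reviewers' fusion status final over the site's assessment.

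**The concern.** Under V.B, missing any one of the three criteria means no success. Under V.E, a level is not fused only if it misses all three. A level with no bridging but little motion, or with bridging and 6° of motion, is a failure under V.B and has no grade under V.E. V.E is the only place that states a not-fused rule, and it is the rule the independent reviewers would apply.

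There are two consequences. Reviewers may settle mixed levels differently from one another. And if mixed levels are left ungraded, V.B offers two exits, carry-forward as fused or exclusion. Both remove failures from the count, which favours the device in a non-inferiority test. The planned sensitivity analysis reverses the exclusions. It does not reverse the carry-forwards, because those patients were never excluded.

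**Working it through.** The documents state no count or frequency on this point, so there is no figure of the plan's own to reproduce.

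**Step 1: enumerate the V.E rules.** Bridging is Present or Absent, angulation is <5° or ≥5°, translation is <3 mm or ≥3 mm, giving 2 × 2 × 2 = 8 patterns.

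| Bridging | Angulation | Translation | V.E grade | V.B success? |
|---|---|---|---|---|
| Present | <5° | <3 mm | Fused | Yes |
| Present | <5° | ≥3 mm | Neither | No |
| Present | ≥5° | <3 mm | Neither | No |
| Present | ≥5° | ≥3 mm | Neither | No |
| Absent | <5° | <3 mm | Neither | No |
| Absent | <5° | ≥3 mm | Neither | No |
| Absent | ≥5° | <3 mm | Neither | No |
| Absent | ≥5° | ≥3 mm | Not Fused | No |

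Six of eight patterns have no grade. Adding Unclear gives 3 × 2 × 2 = 12 patterns: 1 Fused, 1 Not Fused, 10 neither. If Unclear is read as no evidence of bridging, 9 are neither.

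**Step 2: illustrate the exclusion route.** Inputs from the plan: 134 evaluable patients, control rate 80.6% with standard error 2.6%, margin 10 points (Sections V.B and V.G). The true rate is set at the non-inferiority limit, p = 0.806 − 0.10 = 0.706. Expected failures are 134 × 0.294 = 39.4. The share *d* of failures left ungraded and excluded is an assumption.

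Expected primary rate = p / [p + (1 − p)(1 − d)]. For d = 0.10 this is 0.706 / (0.706 + 0.294 × 0.90) = 0.706 / 0.9706 = 0.727.

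The pass probability comes from exact binomial sums: the number fused is Bin(134, 0.706), and each failure is excluded independently with probability *d*. A pass means that the Wald lower 95% limit of (observed rate − 0.806) exceeds −0.10. It is computed with the control fixed, and again with 0.026² added to the variance.

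| Assumed d | Patients excluded | Analysed | Primary rate | Pass, control fixed | Pass, control SE included |
|---|---|---|---|---|---|
| 0% | 0 | 134 | 70.6% | 2.8% | 1.0% |
| 5% | 2.0 | 132 | 71.7% | 5.7% | 2.3% |
| 10% | 3.9 | 130 | 72.7% | 9.7% | 4.4% |
| 25% | 9.8 | 124 | 76.2% | 33% | 21% |

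In these cases the planned sensitivity analysis returns the rate to 70.6%.

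**Step 3: illustrate the carry-forward route.** Suppose a share e = 0.25 of the ungraded failures (again an assumption) had an earlier fused reading and is counted as fused. The planned sensitivity analysis then gives p + (1 − p) × d × e:

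- d = 5%: 0.706 + 0.294 × 0.05 × 0.25 = 71.0%
- d = 10%: 0.706 + 0.294 × 0.10 × 0.25 = 71.3%
- d = 25%: 0.706 + 0.294 × 0.25 × 0.25 = 72.4%

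The sensitivity analysis therefore leaves 0.4 to 1.8 points uncorrected.

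**Step 4: check the repair.** If Not Fused means failure of any one Fused criterion, the 8 patterns become 1 Fused and 7 Not Fused. The 12 patterns become 1 Fused, 10 Not Fused and 1 open (Unclear with both motions below the limits).

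**The case against.** The strongest reply is that this is a gap and not a reversal. No pattern is fused in one section and not fused in the other; V.E's fused rule matches V.B's success definition; and V.B's binary wording already makes every mixed pattern a failure. Harm also needs a chain of events. A reviewer must leave a level blank although only two grades exist. The blank must then be treated as undetermined or missing although all three components were recorded. Carry-forward further requires an earlier fused reading. V.B words its exclusion for missing values, which a mixed pattern does not have. The reviewers' finality is over the site's judgement, not over V.B. The shares used above are assumed, and logical patterns are not patients.

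Much of this stands as a limit on the size of the claim: the route to bias is conditional, and the reviewers' form, which might prevent blanks, is not in the supplied text. It does not remove the defect. If a simple complement had been meant, a separate three-part rule would not have been needed, and the rule as written gives the wrong answer for six of eight patterns of the primary endpoint. Carry-forward is triggered by a status that cannot be determined, which a level meeting neither definition plausibly fits. It is also fair that the patient-level rule and the carry-forward sensitivity analysis would be worth stating even if V.E were correctly worded.

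**Conclusion.** The concern holds and should be fixed. V.E's not-fused rule is incompatible with the binary, all-three endpoint in V.B: 6 of 8 patterns have no grade, and 10 of 12 (or 9, depending on how Unclear is read) once the third bridging grade is included. That conclusion rests on the text alone and needs no assumption.

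The effect on the result cannot be estimated, because no pattern frequencies are given and it is unknown whether mixed levels would be left ungraded. If they were, the direction is clear: the fusion rate rises. On assumed exclusion shares of 5% to 25% of failures, the rise at the non-inferiority limit is 1.1 to 5.6 points, and the chance of a false pass grows from 2.8% to between 5.7% and 33% with the control rate fixed, or from 1.0% to between 2.3% and 21% with its standard error included. These figures show sensitivity and do not predict this trial's result.

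**What to change.** - **Appendix B, V.E:** define Not Fused as failure of any one Fused criterion: bridging Absent, or angular motion ≥5°, or translation ≥3 mm. This applies V.B's own definition and introduces no new threshold.
- **Section V.B:** state that a patient is fused only if every treated level is Fused.
- **Undetermined status:** limit it to missing or unreadable films and to Unclear bridging with both motions below the limits. State one handling for that last pattern and run the other as a sensitivity analysis.
- **Sensitivity analysis:** add one that scores carried-forward patients as not fused.

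The cost is wording in two places and a check that the reviewers' form matches. Status can be derived from the three recorded components, so no new films are required. The downside is that the observed fusion rate may be slightly lower than it would be if mixed levels had gone ungraded.
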